4.10.3.3. Hepatobiliary Events

The percentages of patients with treatment-emergent hepatic AEs will be summarized by treatment group using MedDRA PT nested within each SMQ ordered by decreasing frequency. The following SMQs based on MedDRA will be used to identify hepatic events:

- Broad and narrow terms in the Liver related investigations, signs and symptoms SMQ (20000008)
- Broad and narrow terms in the Cholestasis and jaundice of hepatic origin SMQ (20000009)
- Broad and narrow terms in the Hepatitis non-infections SMQ (20000010)
- Broad and narrow terms in the Hepatic failure, fibrosis and cirrhosis and other liver damage SMQ (20000013)
- Narrow terms in the Liver-related coagulation and bleeding disturbances SMQ (20000015)

4.10.3.4. Injection Site Reactions

Injection site reactions will be evaluated using the spontaneous AE reporting of injection site reactions by the selected MedDRA PTs for the LY3209590 study program.

[Table BDCM.2](#) contains a list of MedDRA PTs based on MedDRA that will be used to identify potential injection site reaction from the spontaneous reported AEs.

The number and percentage of patients experiencing treatment-emergent potential injection site reaction identified using the PTs in [Table BDCM.2](#) will be summarized and compared by treatment group using Fisher's exact test. The number and percentage of patients experiencing treatment-emergent potential injection site reactions that is judged to be related to study drug by the investigator will also be summarized and compared.

Table BDCM.2. List of MedDRA Preferred Terms (PTs) to Search for Injection Site Reaction Adverse Events (AEs)

Preferred Term	Preferred Term Code	Scope
Injection site abscess	10022044	Narrow
Injection site abscess sterile	10022045	Narrow
Injection site atrophy	10022048	Narrow
Injection site erythema	10022061	Narrow
Injection site hypertrophy	10022072	Narrow
Injection site induration	10022075	Narrow
Injection site infection	10022076	Narrow
Injection site inflammation	10022078	Narrow
Injection site irritation	10022079	Narrow
Injection site mass	10022081	Narrow
Injection site edema	10022085	Narrow
Injection site pruritus	10022093	Narrow
Injection site rash	10022094	Narrow
Injection site reaction	10022095	Narrow
Injection site warmth	10022112	Narrow
Injection site cellulitis	10050057	Narrow
Injection site swelling	10053425	Narrow
Injection site discomfort	10054266	Narrow
Injection site nodule	10057880	Narrow
Lipoatrophy	10024604	Narrow
Lipodystrophy acquired	10049287	Narrow
Partial lipodystrophy	10053857	Narrow
Lipohypertrophy	10062315	Narrow
Injection site bruising	10022052	Broad
Injection site haematoma	10022066	Broad
Injection site haemorrhage	10022067	Broad
Injection site pain	10022086	Broad

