## 7. Treatments

### 7.1. Treatments Administered

LY3209590 will be administered once weekly as subcutaneous (SC) injections. Each study participant will receive 1 injection each week, as described in [Table BCDM.3](#). SC injections of LY3209590 will be administered rotating between left and right abdominal regions and upper and lower quadrants. During the first 8 weeks, treatment will be administered by the study staff, while study participants receive education and training on how to reconstitute and self-administer LY3209590. During Weeks 9 to 12, LY3209590 will be reconstituted and administered at the site by the study participant under supervision of the site personnel to assure that the study participant is capable of self-administration. During Weeks 13 to 31, LY3209590 will be self-administered by the study participant at home, or optionally can be administered once weekly by site personnel.

Insulin degludec will be administered once daily at approximately the same time of day, rotating between left and right abdominal regions and upper and lower quadrants.

Study participants will receive treatment with LY3209590 by 1 of 2 algorithms. [Table BCDM.3](#) shows the treatment regimens. See Section [7.2.1](#) for details on dosing algorithms and Section [7.8.1](#) for transitioning to treatment after study completion.

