4.10.3.5. Systemic Hypersensitivity Reaction

The number and proportion of patients experiencing potential treatment-emergent systemic hypersensitivity reactions will be summarized and compared by treatment group using Fisher's exact test. The following MedDRA Standardized MedDRA Query (SMQ) will be used to identify potential systemic hypersensitivity reactions from all TEAEs:

- Anaphylactic reaction (SMQ). Besides using the narrow and broad terms designated within the SMQ, the following search algorithm will also be implemented as another approach to determine if a patient had an anaphylactic reaction: if a patient (had at least 1 event in Category A) or (had at least 1 event that is in Category B and also had at least 1 event that is in Category C) or (had at least 1 event that is in Category D and [also had at least 1 event in Category B or at least 1 event in Category C])
- Angioedema (SMQ)
- Hypersensitivity (SMQ)

Specifically, need to perform the following: (1) any narrow or algorithmic term from any 1 of the 3 SMQs indicated above (i.e., combined search across narrow and algorithmic portions of all 3 SMQs); (2) any narrow scope term within each SMQ, separately (i.e., narrow SMQ search); (3) any term within each SMQ, separately (i.e., broad SMQ search); (4) narrow scope term search within each SMQ, report the PT nested within each SMQ.

Note that an individual patient may contribute multiple events. Also, a single event may satisfy multiple SMQs, in which case the event contributes to every applicable SMQ.

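### The injection site reaction comparison pools Narrow and Broad terms across a weekly and a daily injection regimen, and no patient-level Narrow-only comparison is planned

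*SAP*

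**What the plan says.** SAP 4.10.3.4 draws its events from AE reports: "Injection site reactions will be evaluated using the spontaneous AE reporting of injection site reactions". A participant counts if any listed preferred term is reported: "The number and percentage of patients experiencing treatment-emergent potential injection site reaction identified using the PTs in" SAP Table BDCM.2. That incidence "will be summarized and compared by treatment group using Fisher's exact test". A second analysis repeats the same list for events that the investigator judges drug-related.

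SAP Table BDCM.2 has a Scope column. It marks 23 terms Narrow (for example erythema, induration, nodule and the lipodystrophy terms) and 4 Broad: "Injection site bruising", haematoma, "Injection site haemorrhage" and pain. Nothing in the section refers to that column.

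The next section, SAP 4.10.3.5, does separate scopes for hypersensitivity; one of its required searches is "any narrow scope term within each SMQ, separately (i.e., narrow SMQ search").

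Protocol 7.1 sets the injection schedules. For LY: "Each study participant will receive 1 injection each week". For the comparator: "Insulin degludec will be administered once daily at approximately the same time of day".

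**The concern.** Bruising, bleeding and pain can follow any needle stick. A participant on daily injections has several times as many chances of at least one such event as a participant on weekly injections. A patient-level incidence compared by Fisher's exact test makes no allowance for that.

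Injection site reaction is an adverse event of special interest in both documents (Protocol 10.3.4.6, SAP 4.10.3). Protocol 3.3 names injection-site reactions and lipodystrophy among the potential risks of LY. A reader of the pooled row will want to know whether LY causes more local drug reactions. If needle-trauma events add mainly to the degludec arm, they can offset a real LY excess in the Narrow terms, or give LY an apparent advantage that comes from injecting less often.

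**Working it through.** The documents give no rate, power or sample size for injection site reactions, so there is no stated figure to reproduce. The calculation shows how large the effect could be under stated assumptions.

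**Inputs from the documents**
- LY: one injection a week, the last at Week 31 (Protocol 7.1, 7.8.1). Weeks 0 to 31 give 32 injections.
- Degludec: one a day over the same 32 weeks, 32 × 7 = 224. The ratio is 224/32 = 7.
- About 125 randomised per arm (Protocol 10.1); two-sided alpha 0.10 (SAP 4.1).
- AE analyses run to Visit 801 (SAP 4.10.2), about Week 37. If LY participants inject daily basal insulin from Week 33 to Week 37 (an assumption), the counts are 32 + 28 = 60 and 224 + 35 = 259, a ratio of 259/60 = 4.3.

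**Assumptions**
- The risk q of a reported Broad event per injection is the same in both arms, and injections are independent.
- Narrow events are independent of Broad events.
- Everyone follows the full schedule.

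**Step 1. Broad-term incidence.** With m injections it is 1 − (1 − q)^m. The last two columns give the exact probability that Fisher's test on the Broad terms alone reaches p ≤ 0.10, with 125 per arm.

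| q | LY (32) | Degludec (224) | P(significant), 32 vs 224 | P(significant), 60 vs 259 |
|---|---|---|---|---|
| 0.01% | 0.3% | 2.2% | 0.10 | 0.12 |
| 0.025% | 0.8% | 5.4% | 0.55 | 0.49 |
| 0.05% | 1.6% | 10.6% | 0.90 | 0.83 |
| 0.1% | 3.2% | 20.1% | 0.996 | 0.99 |

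**Step 2. Pooled with Narrow terms.** Pooled incidence is 1 − (1 − Narrow)(1 − Broad). For example, at q = 0.05% with Narrow 8% (LY) and 2% (degludec):
- LY: 1 − 0.92 × 0.984 = 9.5%
- Degludec: 1 − 0.98 × 0.894 = 12.4%

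The direction of the difference has reversed. Exact Fisher probabilities at 32 vs 224 injections, 125 per arm:

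| q | Masking: Narrow 8% vs 2%, P(significant LY excess) | Apparent advantage: Narrow 3% vs 3%, P(any significant difference) |
|---|---|---|
| 0 (Narrow only) | 0.61 | 0.035 |
| 0.01% | 0.28 | 0.10 |
| 0.02% | 0.11 | 0.25 |
| 0.05% | 0.005 | 0.72 |
| 0.1% | 0.000 | 0.98 |

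For every q above 0, nearly all of the last column is degludec higher. In the masking case at q = 0.1%, the pooled test is significant in the opposite direction with probability 0.70. With both LY arms combined (250 vs 125), the masking column falls from 0.78 through 0.40 and 0.15 to 0.005 and 0.000.

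**Step 3. One illustrative trial at q = 0.05%.** Narrow events in 10/125 (LY) and 1/125 (degludec) give p = 0.010. The expected numbers with a Broad event are 125 × 0.016 = 2 and 125 × 0.106 = 13. If no participant has both kinds, the pooled row is 12/125 versus 14/125, p = 0.84.

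**The case against.** **The 7-fold ratio is a treatment-period figure.** This stands. Basal insulin resumed in follow-up, and degludec rescue in LY participants, both narrow it. The 60 versus 259 column shows that the effect shrinks only slightly at a 4.3-fold ratio.

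**The sizes rest on an assumed risk.** This also stands. Over a 10-fold range of q, the probability in Step 1 runs from 0.10 to nearly 1. The arms may also differ per injection: LY is reconstituted from a vial and given by staff or under supervision to Week 12, while degludec is self-injected from a pen. Clustering of events within participants weakens the contrast. With strong gamma heterogeneity (shape 0.1, assumed), the 0.90 at q = 0.05% falls to 0.62, and to 0.49 at 60 versus 259 injections.

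**Fewer injections is a real property of a weekly regimen.** Correct. Pooled incidence is a valid description of regimen burden, so a difference driven by injection count is not an error on that question. A reader might infer that the pooled row is wrong, or that it could manufacture a safety signal against LY. The documents support neither: the surplus of injections is on degludec, so it cannot create an LY excess.

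**The terms are already visible elsewhere.** Partly true. SAP 4.10.2 tabulates treatment-emergent events by preferred term, so each Broad term can be read by arm. One participant can report several terms, so those tables do not yield a patient-level Narrow-only count. The drug-related repeat uses the same pooled list, and in this open-label trial investigators judge relatedness knowing the treatment.

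**Pooling scopes is not unusual in this SAP.** True. SAP 4.10.3.3 takes broad and narrow terms together for four of its five hepatic queries. The contrast with SAP 4.10.3.5 shows that the sponsor has a format for separating scopes, not that it broke a rule.

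**Narrow terms are not free of the problem.** True. Erythema, swelling or discomfort may also rise with injection number, and pain may be a product effect. This is why all three rows are needed.

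**Conclusion.** The point holds in a limited form. SAP 4.10.3.4 tags its terms by scope, pools all 27 in one patient-level comparison, and plans no Narrow-only comparison for a named event of special interest. If the per-injection risk of Broad events is similar in the two arms, the pooled row can hide an LY excess of local drug reactions or show an LY advantage that comes from injection count. At an assumed risk of 0.01% the effect is already visible (chance of detecting 8% versus 2% down from 0.61 to 0.28); at 0.05% detection is almost lost. These sizes are conditional on rates that the documents do not give.

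A reader might infer that this undermines the trial's safety or efficacy conclusions. It does not. Protocol Table BDCM.2 lists injection site reactions under exploratory endpoints, no decision rule in the documents depends on this test, and HbA1c is unaffected. It is a cheap improvement to safety reporting.

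**What to change.** In SAP 4.10.3.4:
- Keep the pooled row and label it as a measure of regimen burden.
- Add a patient-level comparison restricted to the terms marked Narrow in SAP Table BDCM.2.
- Add a separate row for the four Broad terms.
- State that Narrow terms may also depend partly on the number of injections, so the Narrow row reduces the problem and does not remove it.

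The cost is a few lines of wording and two table rows, using a tag already in the SAP and no new data. The downside is that the Narrow row has fewer events and so less precision: even with 8% versus 2%, it detects the excess with probability 0.61 at 125 per arm.

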4.10.3.5. Systemic Hypersensitivity Reaction

The number and proportion of patients experiencing potential treatment-emergent systemic hypersensitivity reactions will be summarized and compared by treatment group using Fisher's exact test. The following MedDRA Standardized MedDRA Query (SMQ) will be used to identify potential systemic hypersensitivity reactions from all TEAEs:

- Anaphylactic reaction (SMQ). Besides using the narrow and broad terms designated within the SMQ, the following search algorithm will also be implemented as another approach to determine if a patient had an anaphylactic reaction: if a patient (had at least 1 event in Category A) or (had at least 1 event that is in Category B and also had at least 1 event that is in Category C) or (had at least 1 event that is in Category D and [also had at least 1 event in Category B or at least 1 event in Category C])
- Angioedema (SMQ)
- Hypersensitivity (SMQ)

Specifically, need to perform the following: (1) any narrow or algorithmic term from any 1 of the 3 SMQs indicated above (i.e., combined search across narrow and algorithmic portions of all 3 SMQs); (2) any narrow scope term within each SMQ, separately (i.e., narrow SMQ search); (3) any term within each SMQ, separately (i.e., broad SMQ search); (4) narrow scope term search within each SMQ, report the PT nested within each SMQ.

Note that an individual patient may contribute multiple events. Also, a single event may satisfy multiple SMQs, in which case the event contributes to every applicable SMQ.

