4.10.2. Adverse Events (AEs)

Adverse events will be summarized as treatment emergent AEs (TEAEs, defined as events that are newly reported after the first dose of study basal insulin or reported to worsen in severity from baseline) for the Safety Population and compared between treatments unless otherwise specified. The Medical Dictionary for Regulatory Activities (MedDRA) Lowest Level Term (LLT) will be used in determination of the treatment-emergent status. The maximum severity for each LLT during the baseline period will be used as baseline severity. All analysis will be performed on the data collected from the date of first dose of study drug to the end of the study (up to Visit 801).

The number and percentage of patients with TEAEs will be summarized by treatment using MedDRA PTs nested within System Organ Class (SOC). Events will be ordered by decreasing frequency within SOC.

The number and percentages of patients with TEAEs ($\geq 2\%$ before rounding) will be summarized by treatment using MedDRA PT (without regard to SOC). Events will be ordered by decreasing frequency.

A TEAE considered possibly related to study drug will be summarized, separately, by treatment group using MedDRA PT nested within SOC. Events will be ordered by decreasing frequency within SOC.

A by-patient listing of all AEs for the Safety Population will be created including, but not limited to, SOC, event PT, severity, and relationship to study drug for all randomized patients.

Discontinuations due to AEs will be summarized by PT and compared between treatment groups using Fisher's exact test for the Safety Population.

Summary of treatment emergent SAEs similar to summaries for the proportion of patients experiencing each reported TEAE by SOC will be included for the Safety Population.

All SAEs (including death) will be listed for the Safety Population.

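### The algorithmic anaphylaxis search in SAP 4.10.3.5 has no time window, so unrelated events months apart are flagged as a potential anaphylactic reaction and enter the combined hypersensitivity count

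*SAP*

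**What the plan says.** Systemic hypersensitivity is one of the adverse events of special interest in SAP 4.10.3. SAP 4.10.3.5 summarises "The number and proportion of patients experiencing potential treatment-emergent systemic hypersensitivity reactions" and compares treatment groups with Fisher's exact test. Three standardised MedDRA queries (SMQs) are used: anaphylactic reaction, angioedema and hypersensitivity.

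For the anaphylactic reaction query, the SAP adds an algorithm to the narrow and broad terms, described "as another approach to determine if a patient had an anaphylactic reaction". A patient meets it in one of three ways:

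- at least one Category A event;
- the patient "had at least 1 event that is in Category B and also had at least 1 event that is in Category C";
- the patient "had at least 1 event that is in Category D and [also had at least 1 event in Category B" or at least one in Category C].

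The section then lists four outputs. Search (1) is the "combined search across narrow and algorithmic portions of all 3 SMQs". Searches (2) and (4) use narrow terms within each query, and search (3) uses any term within each query.

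The queries are applied to all treatment-emergent adverse events. SAP 4.10.2 performs the adverse-event analyses on "data collected from the date of first dose of study drug to the end of the study (up to Visit 801"). SAP 4.1 takes safety data from both treatment and follow-up, whatever the treatment disposition. Protocol 5.1 sets 32 weeks of treatment and 5 weeks of safety follow-up.

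**The concern.** The algorithm asks whether a patient had an anaphylactic reaction, which is a single episode. The rule as written tests something else: whether certain event types ever appear in the same patient's record. Take two patients:

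- Patient 1 has a Category B event in Week 2 and a Category C event in Week 30.
- Patient 2 has a B and a C event on the same day.

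Both are flagged, and the summary count does not separate them.

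The SAP does state timing or sequence in other derived safety definitions. The liver listings in 4.10.4.2 require consecutive blood tests for several criteria, and CGM hypoglycemic episodes in 4.11.3.2 require at least 15 minutes. The protocol also treats a hypersensitivity reaction as one dated event: section 9.4.7 schedules samples near its onset, at its resolution and 30 days later.

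At stake is a between-arm count for a special-interest event in a new weekly insulin. If true cases are few, one or two chance pairings are a material share of that count.

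**Working it through.** **1. Is there a timing condition anywhere?** The B+C and D+(B or C) conditions in 4.10.3.5 are written per patient. They do not require a shared onset date, a maximum interval, a common episode or a link to an injection. Neither 4.1 nor 4.10.2 adds such a condition. Protocol 9.2.2.2 collects extra data on reactions judged related to study drug, but the SAP does not use those data to restrict the algorithm.

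**2. Length of the window.** 32 + 5 = 37 weeks, which agrees with Visit 801 at Week 37 in the Schedule of Activities. 37 × 7 = 259 days. This applies to a participant who completes the schedule.

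**3. Chance hits.** Leaving Category A aside, the rule is the same as having at least two of B, C and D. With independent per-patient incidences b, c and d:

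P = bc + bd + cd − 2bcd

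The documents do not list the category terms or give incidences, so every value of b, c and d below is assumed. The 375 is the planned number randomised.

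| Assumed B/C/D | P | Expected of 375 |
|---|---|---|
| 2/2/1% | 0.0004 + 0.0002 + 0.0002 − 0.000008 = 0.079% | 0.3 |
| 5/4/2% | 0.0020 + 0.0010 + 0.0008 − 0.00008 = 0.37% | 1.4 |
| 8/7/4% | 0.0056 + 0.0032 + 0.0028 − 0.000448 = 1.12% | 4.2 |
| 12/10/6% | 0.0120 + 0.0072 + 0.0060 − 0.00144 = 2.38% | 8.9 |

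These are algorithm hits. Fewer patients are newly added to search (1), because a patient with a B, C or D event that is also a narrow term in any of the three queries is already there.

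**4. How far apart are chance pairs?** Assume two unrelated events fall independently and uniformly over 259 days.

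- Same or adjacent calendar day: (259 + 2 × 258) / 259² = 775 / 67,081 = 1.16%.
- Within 28 days (continuous time): 1 − (1 − 28/259)² = 20.5%, so about 80% are more than four weeks apart.

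The same-or-adjacent-day condition would leave roughly 0.3 × 1.16% = 0.003 to 8.9 × 1.16% = 0.10 chance hits among 375.

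**5. Effect on the between-arm test.** Suppose the chance-hit rate is the same in every arm and there are no true cases. The probability that Fisher's exact test rejects at two-sided 0.10, found by summing over binomial counts, is:

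| Chance-hit rate | 125 vs 125 | 250 vs 125 |
|---|---|---|
| 0.37% | 0.01% | 0.5% |
| 1.12% | 0.7% | 3.4% |
| 2.38% | 2.9% | 6.2% |

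All are below 10%. When true cases exist at rates t₁ and t₀, adding a common chance rate f moves the ratio from t₁/t₀ to about (t₁ + f)/(t₀ + f), which is closer to 1. The size of that dilution needs a true-case rate, which the documents do not give.

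**The case against.** The strongest reply is that this is a deliberately sensitive screen. The section calls its output potential reactions, and the algorithm is only "another approach to determine if a patient had an anaphylactic reaction", alongside the term searches. Over-inclusion in a safety screen errs on the cautious side. The data also allow review: SAP 4.10.2 provides a by-patient listing of all adverse events, and Protocol 9.2.2.2 and 9.4.7 collect reaction details and samples.

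Much of this stands. The label is potential reactions, most of the section's output is untouched, and a flagged patient can be reviewed individually. But case review does not correct the count compared between arms. Section 4.10.3.5 specifies no listing of algorithm hits, and onset date is not among the items named for the adverse-event listing.

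A second reply is that the algorithm is presented as part of a standard query, and that version 2 of the SAP aligned some analysis details with other Phase 2 studies in the programme. Whether the source query has its own timing convention cannot be checked from these documents. The SAP as written states none, and a programmer following it would apply none. It is also fair that no document supports one particular window; the choice belongs to the sponsor.

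A reader might go further and infer that chance pairings would create a false treatment signal, or would make up most algorithm hits. The documents support neither. With a common schedule and equal background rates, the test's error rate is not inflated (step 5). The share of hits due to chance depends on a true-case rate that is neither stated nor derivable.

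**Conclusion.** The point holds as a defect in a stated rule. Followed exactly, SAP 4.10.3.5 flags patients whose B, C or D events are unrelated and months apart, and carries them into combined search (1). Category A hits and searches (2) to (4) are not affected.

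The size is uncertain. Under assumed independent incidences of 2/2/1% to 12/10/6%, about 0.3 to 8.9 of 375 participants would meet the algorithm by chance, with fewer newly added to search (1). About 1.2% of chance pairs would survive a same-or-adjacent-day condition, if events are uniform over 259 days.

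The main consequences are misclassified patients and possible dilution of a true difference between arms. Type I error is not inflated by this alone, provided follow-up and background reporting are equal across arms. The trial is open-label, so equal reporting is itself an assumption, but nothing in the documents shows that it fails. The absence of a window is certain; the practical impact could be well under one patient or several. The change is worth making because it is cheap and the rule does not match its stated purpose.

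**What to change.** In SAP 4.10.3.5, require the B+C, D+B or D+C events to have onset within a short prespecified window. The same or adjacent calendar day is one example. State how partial or missing onset dates are handled. Use this version in search (1), and leave Category A as it is.

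Keep the any-time version as a sensitivity count or listing, showing both onset dates and the date of the last injection, so that wider-spaced pairs can be reviewed.

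The cost is a short addition to the SAP text, one date condition in the program and one listing. No new data collection is proposed. The downside is that a slowly evolving reaction, with onsets further apart than the window, may leave the main count; it would remain visible in the sensitivity listing.
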